9.4.3 ANALYSIS OF THE SECONDARY ENDPOINT(S)

For Secondary Endpoints/Specific Aim 2, we will use multivariate analysis of variance model (MANOVA) with repeated measures. The multivariate outcomes include patient-related outcomes (BPI and PROMIS-10 scores) and PJ PGE₂ concentrations at baseline and day 28. Fixed effect covariates include randomized groups, time, and their interactions. Additional secondary analyses include descriptive analysis and statistical comparison of PJ PGE₂ concentrations at baseline and after secretin administration between the various study groups, and correlations between baseline PJ PGE₂ levels, clinical features, and changes in plasma and saliva PGE₂ levels. Changes in daily pain ratings and narcotic use (in morphine equivalents) will be analyzed in comparison to changes in PJ PGE₂ concentrations. Any dropout before Day 28 will be documented and descriptively summarized. Sensitivity analysis on dropout will be conducted in an exploratory manner according to standard missing data analysis procedure for longitudinal data.¹⁹ As a pilot study, we will collect and descriptively analyze data on feasibility, patient compliance and satisfaction, and attrition, in order to inform the possible future study.

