1 PROTOCOL SUMMARY

1.1 SYNOPSIS

Title:	Phase 1/2 Trial of Indomethacin in Chronic Pancreatitis (The PAIR Trial)
Study Description:	Chronic pancreatitis (CP) is a disabling disease that causes chronic pain, diabetes and malnutrition, and for which there is no effective, disease-modifying medical therapy. Preliminary studies suggest that widely available anti-inflammatory drugs such as indomethacin, which decrease prostaglandin E2 (PGE ₂) production, could be repurposed to lessen the severity of CP. In this prospective, randomized, placebo-controlled study, indomethacin or placebo will be given to patients with CP, and pancreas juice PGE ₂ levels will be measured, in order to determine whether standard doses of indomethacin effectively suppress pancreatic PGE ₂ production and would be suitable for large scale, multicenter trials, with the goal of improving pain and quality of life in patients with this chronic illness.
Objectives:	
Primary Objective: to assess the physiologic effect of orally administered indomethacin (IN) on pancreatic juice PGE₂ concentrations in patients with chronic pancreatitis (CP).
 
Secondary Objectives: A) To correlate drug-induced changes in pancreatic juice PGE₂ levels with changes in salivary and blood PGE₂ levels, blood IN levels, and changes in patient-reported pain outcome (PRO) and quality of life (QOL), and B) to establish a basis for subsequent multicenter clinical trials of chronic COX-2 inhibition in CP.

Specific Aims:	1. To obtain steady-state pharmacologic data assessing the magnitude and variability of change in pancreas juice, blood, and saliva PGE ₂ concentrations after administration of oral IN or placebo to CP patients for 28 days. 2. To correlate changes in pancreas juice PGE ₂ concentrations with changes in PRO and QOL after 28 days of study drug administration. Endpoints:
	Primary Endpoint: Decrease in mean pancreatic juice PGE ₂ concentration after indomethacin treatment, to no more than 66% of baseline, and statistically significant in comparison to placebo. Secondary Endpoints: Correlation of pancreatic juice, blood, and saliva PGE ₂ levels; correlation of post-treatment decreases in pancreas juice PGE ₂ concentrations with improvements in patient-reported outcomes (pain and quality of life).

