9 STATISTICAL CONSIDERATIONS

9.1 STATISTICAL HYPOTHESES

Primary Endpoint:

- Decrease in mean pancreatic juice PGE₂ concentration after indomethacin treatment, to no more than 66% of baseline, and statistically significant in comparison to placebo.

Secondary Efficacy Endpoints:

- Changes in salivary and blood PGE₂ concentrations after study drug administration will have statistically significant correlation with changes in PJ PGE₂ concentrations and blood IN levels.
- Salivary and blood PGE₂ concentrations will have statistically significant correlation with PJ PGE₂ concentrations.
- Improvement in pain and quality of life of study participants will have statistically significant correlation with post-treatment changes in PJ PGE₂ concentrations.
- Exploratory analysis of molecular analytes (cytokine and microbiome) in blood and saliva will be done to measure effect of IN administration.

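### The MANOVA tests named for Specific Aim 2 compare mean vectors between arms; they do not test whether PGE2 change correlates with change in pain and quality of life, and no other stated method does so for BPI or PROMIS-10.

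*Combined protocol and SAP*

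**What the plan says.** The target is stated consistently. Specific Aim 2 in the synopsis (1.1) reads "To correlate changes in pancreas juice" PGE2 concentrations "with changes in PRO and QOL after 28 days of study drug administration". Section 9.1 makes it a hypothesis with a significance criterion: "Improvement in pain and quality of life of study participants will have statistically significant correlation with post-treatment changes in PJ PGE₂ concentrations". The secondary endpoint in section 3 and the third exploratory hypothesis in 4.1 ask for the same association.

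The method is given in 9.4.3 and, in the same words, in the statistical part of 4.1: "we will use multivariate analysis of variance model (MANOVA) with repeated measures". On the outcome side, "The multivariate outcomes include patient-related outcomes (BPI and PROMIS-10 scores) and PJ" PGE2 at baseline and day 28. On the effect side, "Fixed effect covariates include randomized groups, time, and their interactions".

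Two further sentences of 9.4.3 come near the target. One lists correlations between baseline PGE2 "levels, clinical features, and changes in plasma and saliva" PGE2; BPI and PROMIS-10 are not among them. The other says that changes in diary pain and opioid use will be compared with PGE2 changes, without a method.

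Section 9.4.2 allows questionnaire data to be analysed with the random intercept model used for PGE2. Section 9.4.9 calls the patient-reported and quality-of-life analyses exploratory and says they are meant to support sample size planning for later studies.

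**The concern.** Aim 2 asks whether patients whose PGE2 falls more also improve more. The group, time and interaction terms of the MANOVA ask whether the vector of means differs between arms or changes over time. PGE2 is the variable the drug is expected to move and it sits in that vector, so it can make the joint test significant by itself. In the other direction, a strong patient-level association with no difference between arms leaves the test at its nominal error rate.

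The risk is that a significant MANOVA, reported under Aim 2, is read as evidence linking PGE2 suppression to symptom benefit, or that a null one is read as evidence against a link. Either would feed poor information into the design of the next study.

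**Working it through.** **Inputs from the documents (9.2).** 16 per arm, or 12 after data loss; PGE2 level 307 pg/ml (a median, used here as the mean); SD 84 pg/ml; one-third reduction = 307/3 = 102.3 pg/ml; two-sided alpha 0.05. Section 9.4.1 prints a different significance threshold, which is a separate matter; 0.05 is used here.

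**Assumptions not in the documents.** Correlation ρ of PGE2 between baseline and day 28 from 0 to 0.7; 3 or 5 outcome components, since the plan does not say how many scores each questionnaire contributes; multivariate normal changes.

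**Step 1: the plan's own figures.** The plan states no power for Aim 2. For the primary comparison, the normal approximation Φ(d/(SD·√(2/n)) − 1.96) gives:
- 50% reduction, n = 16: 153.5/29.70 − 1.96 = 3.21, power 0.999 (stated 0.998).
- One-third reduction, n = 16: 102.3/29.70 − 1.96 = 1.49, power 0.931 (stated 0.94).
- One-third reduction, n = 12: 102.3/34.29 − 1.96 = 1.02, power 0.847 (stated 0.85).

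The inputs are therefore read as the plan intended. (The exact t-test gives 0.999, 0.915 and 0.814.)

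**Step 2: the MANOVA when only PGE2 moves.** With two time points, the group-by-time test is Hotelling's T² on the vector of changes. The SD of PGE2 change is 84·√(2(1 − ρ)). With no effect on the questionnaires and no correlation of their changes with PGE2 change, the noncentrality is λ = (n/2)·(102.3/SD of change)², referred to a noncentral F with p and 2n − p − 1 degrees of freedom. For example, at ρ = 0.5 and n = 16, the SD of change is 84.0 and λ = 8 × (102.3/84)² = 11.9.

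| ρ | SD of change | λ, n = 16 | 16/arm, p = 3 | 16/arm, p = 5 | 12/arm, p = 3 | 12/arm, p = 5 |
|---|---|---|---|---|---|---|
| 0 | 118.8 | 5.9 | 45% | 35% | 33% | 25% |
| 0.3 | 99.4 | 8.5 | 62% | 50% | 46% | 35% |
| 0.5 | 84.0 | 11.9 | 78% | 66% | 61% | 48% |
| 0.7 | 65.1 | 19.8 | 95% | 89% | 85% | 73% |

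Simulation (20,000 trials; ρ = 0.5, p = 3, questionnaire changes correlated 0.5 with each other) gives 78% at 16 per arm and 61% at 12.

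**Step 3: a real association and no arm difference.** In the same simulation, with a true correlation of 0.6 between PGE2 change and each questionnaire change and no group effect, the MANOVA rejects about 5% at either sample size.

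**Step 4: a direct test.** Take the correlation r of changes after centring within arm, with t = r·√(df/(1 − r²)) and df = 2n − 3. It rejects about 5% when the true correlation is 0, even with the full PGE2 effect present. With a true correlation of 0.6 it rejects 96% (n = 16) or 89% (n = 12).

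**Step 5: precision.** By Fisher's z with one covariate, the standard error is 1/√(N − 4).
- The correlation detectable with 80% power is tanh((1.96 + 0.84)/√28) = 0.485 at N = 32, and 0.556 at N = 24.
- An observed r of 0.4 at N = 32 has a 95% interval of tanh(0.424 ± 0.370), or 0.05 to 0.66.

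**Step 6: why arm must be in the model.** Suppose the drug also shifts a symptom score by 1 SD (an assumption) with no within-arm correlation. At 16 per arm and ρ of 0.3 to 0.7, a correlation pooled over arms averages 0.21 to 0.28 and is significant in 21-35% of simulated trials. The arm-adjusted version stays at about 5%.

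**The case against.** The strongest reply is that the model already contains the answer. Once group means are removed, the error covariance of the changes in a joint model of PGE2, BPI and PROMIS-10 gives exactly the arm-adjusted correlation; centring within arm and partialling out arm are the same operation. A reader might infer that the planned model cannot answer Aim 2, and that would go too far. What stands is that neither 9.4.3 nor 4.1 says this quantity will be extracted, tested or given an interval. The only correlation the plan says it will read from a model is the intra-subject one under Aim 1.

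A reader might also infer that the next trial depends on this analysis. It does not: 4.1 rests that decision on a significant PGE2 fall of at least one third, and 9.4.9 labels these outcomes exploratory.

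Nor are the rejections in Step 2 false positives. In that scenario the drug does lower PGE2, so the joint null is false. The harm arises only if the joint p-value is read as evidence of a correlation.

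The comparison of diary pain and opioid use with PGE2 change does bear on the pain half of the aim, but it has no stated method and leaves out both questionnaires. The pooled correlation in Step 6 is not something the plan specifies for BPI or PROMIS-10; it is shown only to explain the form of the fix.

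Finally, the secondary objective speaks of drug-induced changes, and adjusting for arm removes the between-arm part. That is a fair point about the estimand. But the between-arm part is a single contrast: any two measures that the drug moves will correlate through it, whether or not they are linked within patients.

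**Conclusion.** The concern holds in a limited form. The tests of the method named for Aim 2 do not test the association that Aim 2 and 9.1 specify, and no other stated analysis does so for BPI or PROMIS-10.

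The size depends on assumptions the documents do not supply. With a PGE2 effect alone, the group-by-time test rejects in 45-95% of trials at 16 per arm with three outcomes, and in 25-95% over within-subject correlations of 0 to 0.7, three to five outcomes and 12 to 16 per arm. A claim that it will usually be significant is therefore not secure at the low end. The insensitivity in the other direction (about 5% at a true correlation of 0.6 with no arm difference) was simulated at a within-subject correlation of 0.5 with three outcomes.

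The consequence is confined to a secondary, exploratory conclusion that informs planning. The primary analysis and the go decision are untouched.

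**What to change.** Amend 9.4.3 and the matching text in 4.1 before unblinding:

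- State that the Aim 2 analysis is the association of change in BPI, and separately change in PROMIS-10, with change in pancreatic juice PGE2 (on the scale chosen under 9.4.2), with treatment arm in the model. Report it as a partial correlation, equivalently the MANOVA residual correlation of changes, with a 95% confidence interval.
- Use the same method for diary pain and opioid use.
- Show an unadjusted correlation pooled over arms, if at all, as descriptive only.
- State that the joint MANOVA p-value will not be taken as evidence of a link between PGE2 and symptoms.
- Analyse the treatment effect on each questionnaire score with the 9.4.2 model, which that section already permits.

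The cost is plan wording and one degree of freedom for arm. No new data are needed, and the interval serves the planning purpose stated in 9.4.9.

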9.4.4 SAFETY ANALYSES

The frequency and severity of AEs in the placebo and IN groups will be calculated and compared statistically. Because IN is a common medication that has been in use for many decades its adverse effect profile is already well known, and we do not expect data from this pilot study to materially change our understanding of its adverse effects.

9.4.5 BASELINE DESCRIPTIVE STATISTICS

Baseline descriptive statistics will compare the IN and placebo groups on variables including age, gender, cause of pancreatitis (if known), time since the most recent episode of acute pancreatitis requiring

hospitalization, presence and duration of diabetes, exocrine insufficiency, pancreas enzyme replacement therapy (PERT) and history of occasional NSAID or ASA use.

9.4.6 PLANNED INTERIM ANALYSES

Not applicable.

9.4.7 SUB-GROUP ANALYSES

Not applicable.

9.4.8 TABULATION OF INDIVIDUAL PARTICIPANT DATA

Study data will be tabulated in electronic databases and spreadsheets.

9.4.9 EXPLORATORY ANALYSES

Analyses of patient-reported outcomes (PRO) and quality of life (QOL) data are exploratory, and meant to form a basis for sample size calculation for subsequent larger clinical studies.

10 SUPPORTING DOCUMENTATION AND OPERATIONAL CONSIDERATIONS

10.1 REGULATORY, ETHICAL, AND STUDY OVERSIGHT CONSIDERATIONS

10.1.1 INFORMED CONSENT PROCESS

10.1.1.1 CONSENT/ASSENT AND OTHER INFORMATIONAL DOCUMENTS PROVIDED TO PARTICIPANTS

Consent forms describing in detail the study intervention, study procedures, and risks are given to the participant and written documentation of informed consent is required prior to starting intervention/administering study intervention. Consent materials are attached to this study protocol and IRB application.

10.1.1.2 CONSENT PROCEDURES AND DOCUMENTATION

[Informed consent is a process that is initiated prior to the individual's agreeing to participate in the study and continues throughout the individual's study participation. Consent forms will be Institutional Review Board (IRB)-approved and the participant will be asked to read and review the document. The investigator will explain the research study to the participant and answer any questions that may arise. A verbal explanation will be provided in terms suited to the participant's comprehension of the purposes, procedures, and potential risks of the study and of their rights as research participants. Participants will have the opportunity to carefully review the written consent form and ask questions prior to signing. The participants will have the opportunity to discuss the study with their family or

surrogates or think about it prior to agreeing to participate. The participant will sign the informed consent document prior to any procedures being done specifically for the study. Participants must be informed that participation is voluntary and that they may withdraw from the study at any time, without prejudice. A copy of the informed consent document will be given to the participants for their records. The informed consent process will be conducted and documented in the source document (including the date), and the form signed, before the participant undergoes any study-specific procedures. The rights and welfare of the participants will be protected by emphasizing to them that the quality of their medical care will not be adversely affected if they decline to participate in this study.

10.1.2 STUDY DISCONTINUATION AND CLOSURE

This study may be temporarily suspended or prematurely terminated if there is sufficient reasonable cause. Written notification, documenting the reason for study suspension or termination, will be provided by the suspending or terminating party to the IRB, FDA, and NIH. If the study is prematurely terminated or suspended, the Principal Investigator (PI) will promptly inform study participants, the Institutional Review Board (IRB), and sponsor and will provide the reason(s) for the termination or suspension. Study participants will be contacted, as applicable, and be informed of changes to study visit schedule.

Circumstances that may warrant termination or suspension include, but are not limited to:

- Determination of unexpected, significant, or unacceptable risk to participants
- Demonstration of efficacy that would warrant stopping
- Insufficient compliance to protocol requirements
- Data that are not sufficiently complete and/or evaluable
- Determination that the primary endpoint has been met
- Determination of futility

Study may resume once concerns about safety, protocol compliance, and data quality are addressed, and satisfy the sponsor, IRB and/or Food and Drug Administration (FDA).

10.1.3 CONFIDENTIALITY AND PRIVACY

Participant confidentiality and privacy is strictly held in trust by the participating investigators, their staff, and the sponsor(s) and their interventions. This confidentiality is extended to cover testing of biological samples and genetic tests in addition to the clinical information relating to participants. Therefore, the study protocol, documentation, data, and all other information generated will be held in strict confidence. No information concerning the study or the data will be released to any unauthorized third party without prior written approval of the sponsor.

All research activities will be conducted in as private a setting as possible.

The study monitor, other authorized representatives of the sponsor, representatives of the Institutional Review Board (IRB), regulatory agencies or pharmaceutical company supplying study product may inspect all documents and records required to be maintained by the investigator, including but not limited to, medical records (office, clinic, or hospital) and pharmacy records for the participants in this study. The clinical study site will permit access to such records.

The study participant's contact information will be securely stored at each clinical site for internal use during the study. At the end of the study, all records will continue to be kept in a secure location for as long a period as dictated by the reviewing IRB, Institutional policies, or sponsor requirements.

Study participant research data, which is for purposes of statistical analysis and scientific reporting, will be transmitted to and stored in a password-protected study RedCap database that is accessible to the study teams at both Mayo Clinic and OSU. This will not include the participant's contact or identifying information. Rather, individual participants and their research data will be identified by a unique study identification number. The study data entry and study management systems used by clinical sites will be secured and password protected. At the end of the study, all study databases will be de-identified and archived at Mayo Clinic.

10.1.4 FUTURE USE OF STORED SPECIMENS AND DATA

Data collected for this study will be analyzed and stored at Mayo Clinic and Ohio State University. After the study is completed, the de-identified, archived data will be transmitted to and stored at Mayo Clinic and/or Ohio State University, for use by other researchers including those outside of the study. Permission to transmit data to Mayo Clinic will be included in the informed consent.

With the participant's approval and as approved by local Institutional Review Boards (IRBs), de-identified biological samples will be stored at Mayo Clinic and/or Ohio State University with the same goal as the sharing of data. These samples could be used to research the causes of pancreatic disease, its complications and other conditions for which individuals with pancreatitis are at increased risk, and to improve treatment. Biospecimens will be labelled with a code-link that will allow linking the biological specimens with the phenotypic data from each participant, maintaining the blinding of the identity of the participant.

During the conduct of the study, an individual participant can choose to withdraw consent to have biological specimens stored for future research. However, withdrawal of consent with regard to biosample storage may not be possible after the study is completed.

When the study is completed, access to study data and/or samples will be provided by joint review and decision of the study PIs at Mayo Clinic and Ohio State University.

If a PI moves to a new institution, attempts will be made to transfer the relevant portion of the grant to the new institution. In the event that a PI cannot carry out his/her duties, a new PI will be recruited as a replacement at one of the participating institutions.

10.1.6 SAFETY OVERSIGHT

Safety oversight will be under the direction of a Data and Safety Monitoring Board (DSMB) composed of individuals with the appropriate expertise, including one gastroenterologist at Mayo Clinic and one gastroenterologist at Ohio State University. Members of the DSMB will be independent from the study conduct and free of conflict of interest. The DSMB will meet (by telephone or video conference) at least quarterly to assess safety and efficacy data of the study, and will meet as needed when informed of study SAEs or UPs. The DSMB will provide its input to the study PIs and IRB, and generate a quarterly DSMB report.

The charter of the DSMB is to:

- 1) Review all SAEs and UPs in a timely fashion, as detailed in sections 8.3 and 8.4 of this protocol.
- 2) To halt study activities (including drug administration and endoscopic procedures) pending IRB and FDA review if 2 or more SAEs have occurred that, in the opinion of the DSMB, are definitely or probably related to study participation.

- 3) To advise the study PIs regarding changes to the study protocol and/or ICF in response to AEs, SAEs and UPs.
- 4) Generate a quarterly report based on data provided by study staff.

The quarterly DSMB report will be sent to the study staff including the PIs, and will be included in reports to IRB, FDA and NIH. The quarterly report will include:

- a. A summary of study recruitment, enrollment, and participant completion
- b. A summary of all AEs, SAEs and UPs that have occurred since the last quarterly report and in total for the study
- c. Recommendations regarding study protocol or ICF modification, study suspension or discontinuation.

